## **7.2 CONCOMITANT DISEASES AND MEDICATION**

Frequency tables are planned for this section of the report, based on the TS.

Concomitant diseases will be coded using the latest version of the coding system of the Medical Dictionary for Drug Regulatory Activities (MedDRA). Medications will be coded using the latest version of the World Health Organization Drug Dictionary (WHO-DD). The coding version number will be displayed as a footnote in the respective output.

The diagnoses and medications will be listed. Subjects without any concomitant diagnoses or concomitant therapies should be marked with a “No” in the respective column.

The relevance of the concomitant therapies to the evaluation of PK will be decided no later than at the RPM/DBLM.

## **7.3 TREATMENT COMPLIANCE**

**Section 4.3 of the CTP:** *Compliance will be assured by administration of all trial medication in the study centre under supervision of the investigating physician or a designee. The measured plasma concentrations will provide additional confirmation of compliance.*

It is not intended to list the compliance separately. Any deviations from complete intake will be addressed in the RPM/DBLM and described in the CTR.

## **7.4 PRIMARY ENDPOINTS**

Refer to TSAP [Section 7.8](#) for a description of the analysis of safety and tolerability of BI 730357.

## **7.5 SECONDARY ENDPOINTS**

### **7.5.1 Key secondary endpoints**

This section is not applicable as no key secondary endpoints have been specified in the protocol.

**7.5.2 Secondary endpoints**

## **7.7 EXTENT OF EXPOSURE**

Descriptive statistics are planned for this section of the report based on the TS. The date and time of drug administration will be listed for each subject.

## **7.8 SAFETY ANALYSIS**

All safety analyses will be performed on the TS.

If not stated otherwise, the safety results will be sorted by treatment group.

The safety data for treated subjects who failed to complete the study (dropouts or withdrawals) will be reported as far as their data are available. All withdrawals will be documented and the reason for withdrawal recorded.

### **7.8.1 Adverse events**

AEs will be coded with the most recent version of MedDRA.

The analyses of AEs will be descriptive in nature and will be based on BI standards as presented in the corporate guideline: “Analysis and Presentation of Adverse Event Data from Clinical Trials” [001-MCG-156] (9).

The standard AE analyses will be based on the number of subjects with AEs (and not on the number of AEs).

For analysis, multiple AE occurrence data on the electronic case report form (eCRF) will be collapsed into an AE provided that all of the following applies:

- All AE attributes are identical (lower level term (LLT), intensity, action taken, therapy required, seriousness, reason for seriousness, relationship, outcome, AE of special interest (AESI))
- The occurrences were time-overlapping or time-adjacent (time-adjacency of two occurrences is given if the second occurrence started within one hour after end of the first occurrence)

For further details on summarization of AE data, please refer to [001-MCG-156] (9).

**Section 5.2.6.1.4 of the CTP:** *The following are considered as AESIs:*

- **Hepatic injury**  
*A hepatic injury is defined by the following alterations of hepatic laboratory parameters:*
  - *An elevation of AST (aspartate aminotransferase) and/or ALT (alanine aminotransferase)  $\geq 3$ -fold ULN combined with an elevation of total bilirubin  $\geq 2$ -fold ULN measured in the same blood sample, or*
  - *Aminotransferase (ALT and/or AST) elevations  $\geq 10$ -fold ULN*

*These lab findings constitute a hepatic injury alert and the subjects showing these lab abnormalities need to be followed up according to the ‘DILI checklist’ provided in the ISF. In case of clinical symptoms of hepatic injury (icterus, unexplained encephalopathy, unexplained coagulopathy, right upper quadrant abdominal pain, etc.) without lab results (ALT, AST, total bilirubin) available, the Investigator should make sure that these parameters are analysed, if necessary in an unscheduled blood test. Should the results meet the criteria of hepatic injury alert, the procedures described in the DILI checklist should be followed.*

The analysis of adverse events will be based on the concept of treatment emergent AEs.

**Section 1.2.6 of the CTP:** *The residual effect period (REP) for BI 730357 is not known at this early stage of development and therefore conservatively defined as 7 days.*

### **Section 7.3.4 of the CTP:**

*Therefore, measurements planned or AEs recorded prior to intake of trial medication will be assigned to the screening period, those between trial medication intake and end of REP [...] will be assigned to the treatment period. Events occurring after the REP but prior to trial termination date will be assigned as 'follow-up'.*

For more details see the TSAP ADS plan.

According to ICH E3 ([10](#)), AEs classified as 'other significant' needs to be reported and will include those non-serious and non-significant adverse events with

- (i) 'action taken = discontinuation' or 'action taken = reduced', or
- (ii) marked haematological and other lab abnormalities or lead to significant concomitant therapy as identified by the investigator or Clinical Trial Leader.

An overall summary of AEs (including AESIs) will be presented.

The frequency of subjects with AEs will be summarized by treatment, primary system organ class (SOC) and preferred term (PT), as well as by treatment, worst intensity, primary SOC and PT. Separate tables will be provided for subjects with other significant AEs according to ICH E3 ([10](#)), for subjects with serious AEs, for subjects with drug-related AEs, for subjects with drug related serious adverse events and for subjects with AESIs.

The SOC and PTs will be sorted by frequency (within SOC). The MedDRA version number will be displayed as a footnote in the respective output.

In addition, frequencies of subjects with non-serious AEs that had an incidence of > 5% for at least one treatment will be summarised by treatment, primary SOC and PT.

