#### **4.1.5 Blinding and procedures for unblinding**

##### **4.1.5.1 Blinding**

The trial is designed double-blind. The treatments administered (active or placebo) will be blinded to the subjects and the investigators (outcome assessors) in order to limit the occurrence of any bias which the knowledge of treatment may have. According to the rising dose design, the current dose level will be known to subjects and investigators.

Proprietary confidential information © 2018 Boehringer Ingelheim International GmbH or one or more of its affiliated companies

At the sponsor's site, access to the randomisation schedule is restricted to the randomisation operators, the Clinical Trial Support group and the Pharmaceutics Department.

The trial pharmacokineticist may receive the randomisation codes prior to official unblinding to perform the preliminary PK analysis. He or she will confirm in writing that the codes will be treated confidentially.

In addition, regarding the sponsor, all trial data will be handled open label. This means that trial functions of the sponsor are unblinded (trial clinical leader, data manager, statistician, bioanalyst, pharmacokineticist as well as dedicated CRO personnel). This is acceptable because they are neither in contact with subjects nor with site staff.

Within the central ECG lab, the staff involved with interval measurements and morphological analyses will be blinded with respect to the treatment and also with regard to the recording date and time as well as planned time points of the ECGs. The interval measurements for a given subject will be performed in a random and blinded sequence by a single technician.

Access to the randomisation schedule will be controlled and documented by a signed confidentiality statement, which will be stored in the TMF.

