### **6.2.2 Treatment period**

Each subject will receive one dose of the respective trial medication (BI 730357 or placebo) at Visit 2.

Trial medication will be taken orally by each subject under direct supervision of the investigator or designee. Details on treatments and procedures of administration are described in Section [4.1.4](#).

Study participants will be admitted to the trial site in the evening of Day -1 and kept under close medical surveillance for at least 48 hours following the drug administration. The subjects will then be allowed to leave the trial site after formal assessment and confirmation of their fitness by the investigator or his designee. On all other study days, the study will be performed in an ambulatory fashion.

For details on time points and procedures for collection of plasma and urine samples for PK analysis, refer to [Flow Chart](#).

The safety measurements performed during the treatment period are specified in Section [5.2](#) and in the [Flow Chart](#). For details on time points for all other trial procedures, refer to the [Flow Chart](#). AEs and concomitant therapy will be assessed continuously from screening until the end of study examination.

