### **7.8.2      Laboratory data**

The analyses of laboratory data will be descriptive in nature and will be based on BI standards [001-MCG-157] ([11](#)).

Laboratory data will be analysed qualitatively via comparison of laboratory data to their reference ranges. Values outside the reference range as well as values defined as possible clinically significant will be flagged in the data listings.

It is the investigator's responsibility to decide whether a lab value is clinically significant abnormal or not (at the RPM/DBLM at the latest).

Descriptive statistics of laboratory data will be calculated by planned time point based on the worst value of the subject at that planned time point (or assigned to that planned time point).

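### After a single dose, the table of other significant AEs rests in effect on criterion (ii), and SAP 7.8.1 lets the unblinded Clinical Trial Leader add events to it

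*SAP*

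**What the plan says.** SAP 7.8.1 sets two routes by which a non-serious AE becomes other significant in the sense of ICH E3, and gives the class its own table by treatment.

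- Criterion (i) looks at what was done with the drug: "action taken = discontinuation' or 'action taken = reduced".
- Criterion (ii) is a judgement: "marked haematological and other lab abnormalities or lead to significant concomitant therapy as identified by the investigator or Clinical Trial Leader".

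On dosing, Protocol 6.2.2 states: "Each subject will receive one dose of the respective trial medication (BI 730357 or placebo) at Visit 2".

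On blinding, Protocol 4.1.5.1 says that the treatments "will be blinded to the subjects and the investigators (outcome assessors", while at the sponsor all data are handled open label and the "trial functions of the sponsor are unblinded (trial clinical leader, data manager, statistician, bioanalyst, pharmacokineticist as well as dedicated CRO personnel". The reason given is: "This is acceptable because they are neither in contact with subjects nor with site staff".

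On laboratory values, SAP 7.8.2 says that "values defined as possible clinically significant will be flagged in the data listings", and leaves it to the investigator to decide whether a value is clinically significant.

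**The concern.** One of the two criteria is close to objective: a recorded action on the drug. In a single-dose trial it has almost nothing to act on. What remains is a criterion built on the words marked and significant, for which the SAP sets no threshold, and one of its two named judges knows who received active drug.

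Safety and tolerability are the main objective, and the investigator is blinded to active or placebo precisely to limit bias from knowing the treatment. An open route for an unblinded role to nominate events for a by-treatment safety table works against that. With arms of six, a single nomination is visible.

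There is also a gap in coverage. Because (i) is tied to drug action, an AE that makes a subject leave the trial early need not enter the table at all.

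**Working it through.** The plan states no figure for this point, so there is nothing to reproduce. The check sets the sections side by side and then works out the weight of one subject.

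**Can criterion (i) operate?**
1. Protocol 6.2.2 and the product tables in 4.1.1: one administration, on Day 1. After it, no dose remains to be stopped or reduced.
2. Protocol 3.3.4: a subject who leaves before dosing is neither entered in the CRF nor reported. A pre-dose discontinuation therefore cannot fill (i) either.
3. Protocol 3.3.4.1 keeps general rules for discontinuing treatment, but provides no second administration to which they could apply.

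Criterion (i) is thus in practice inoperative, and the table depends in effect on (ii).

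**Who fills criterion (ii)?**
1. SAP 7.8.1 names the investigator or the Clinical Trial Leader (CTL).
2. Protocol 4.1.5.1: the investigator is blinded to active or placebo, and the trial clinical leader is unblinded.
3. Neither document says that the selection is fixed before treatment is known, that the investigator's view prevails, or that CTL nominations are marked.
4. The justification for the open sponsor is lack of contact with subjects and site staff. That does not address choosing events for a table by treatment. It also sits badly with Protocol 1.4 and 3.1, where the CTL performs and minutes the safety reviews with the principal investigator. Protocol 6.1 calls the report planning meeting blinded, which does not fit an open sponsor team.

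**What can the CTL's role do?** The two judges are joined by *or*. Relative to the investigator's own selection, the CTL can add an event but is given no power to strike one out. A column can therefore only go up. Additions made in one arm and not in another would still change the comparison between arms.

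**Weight of one subject** (group sizes from Protocol 3.1):
- Each dose group: 6 on active drug; 1/6 = 16.7 percentage points.
- Pooled placebo: 3 × 2 = 6; 1/6 = 16.7 points.
- BI total: 3 × 6 = 18; 1/18 = 5.6 points.

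These figures show how coarse the table is. They are not an estimate of bias.

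**The case against.** The case against giving this much weight is substantial, and most of it stands.

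- **The investigator comes first.** A reader might infer that the table is selected with treatment known. The documents do not support that: the blinded investigator is the first-named judge, and the text only allows an unblinded role to contribute.
- **No veto.** A reader might also infer that the CTL could lower an arm's rate. Nothing gives the CTL power to remove an event.
- **Blinded steps come earlier.** Under Protocol 5.2.6.1.1 a laboratory change becomes an AE only if the investigator judges it clinically relevant, and under 5.2.6.2.1 the investigator keeps the AE record. In SAP 7.8.1 the phrase naming the two judges may attach only to concomitant therapy. Since SAP 7.8.2 gives laboratory significance to the investigator, the CTL's part in the laboratory branch is uncertain.
- **Little is lost.** No hypothesis is tested, and the AE analysis is descriptive. The primary endpoint, subjects with drug-related AEs, does not use this class. All AEs are tabulated by system organ class (SOC) and preferred term (PT) and by worst intensity, with separate tables for serious, drug-related and special-interest events. Withdrawals and their reasons are documented in any case.
- **The open sponsor is disclosed.** Protocol 4.1.5.1 states it openly, and Amendment 1 added text on it.

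It is also tempting to replace (ii) with laboratory limits and the recorded attribute for therapy required. That goes too far. The limits are in a sponsor guideline that is not among the documents, and no field is shown that links an AE to a flagged value. Any treated headache, the most frequent event in the first-in-human trial, would enter a table meant for significant therapy.

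What survives is narrower: one criterion that cannot work as written, and a second that is open to an unblinded nomination with no step to fix or label it.

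**Conclusion.** The point holds in a limited form. Criterion (i) is in practice inoperative after dosing, so the table depends in effect on (ii), and through (ii) it can be added to, in part, by someone who knows the treatment. One such addition is worth 16.7 percentage points in a dose group or in pooled placebo, and 5.6 in the BI total. The effect stays within one descriptive table and does not reach the primary endpoint or the main AE tables. This is a cheap improvement, not a threat to the trial's conclusions.

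The conclusion rests on these assumptions:
- The trial clinical leader of Protocol 4.1.5.1 and the Clinical Trial Leader of SAP 7.8.1 are the same role. The protocol's abbreviation list and its section 1.4 support this.
- The CRF does not code the action taken in some way that lets a single-dose subject count as discontinued. That coding is not shown, so the statement that (i) is empty is a sound inference and not something the documents say.
- The sponsor's AE guideline, to which SAP 7.8.1 defers for detail, contains no masking step for the CTL. It is not available here.

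**What to change.** In SAP 7.8.1:

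1. Delete the Clinical Trial Leader from criterion (ii), so that the blinded investigator alone identifies events. If the sponsor wants to keep the CTL's review, require that the investigator's selection is fixed and documented before any unblinded role contributes, and mark CTL additions as such in the table or a footnote.
2. Add to criterion (i) AEs recorded as the reason for premature withdrawal from the trial. Protocol 3.3.4 and SAP 7.8 already require that reason to be recorded, and Protocol 5.2.4.1 foresees removing a subject for an ECG abnormality, so the case can arise.
3. Keep the word significant for concomitant therapy, as judged by the blinded investigator. Do not replace it with any therapy given.
4. State whether the phrase on who identifies the events covers both the laboratory and the therapy branch, so that 7.8.1 agrees with 7.8.2.

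The cost is a few lines of SAP text and the use of a withdrawal reason that is already collected. The downside is that the CTL's additional review no longer feeds the table directly, or does so only as a labelled addition.

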### **7.8.2      Laboratory data**

The analyses of laboratory data will be descriptive in nature and will be based on BI standards [001-MCG-157] ([11](#)).

Laboratory data will be analysed qualitatively via comparison of laboratory data to their reference ranges. Values outside the reference range as well as values defined as possible clinically significant will be flagged in the data listings.

It is the investigator's responsibility to decide whether a lab value is clinically significant abnormal or not (at the RPM/DBLM at the latest).

Descriptive statistics of laboratory data will be calculated by planned time point based on the worst value of the subject at that planned time point (or assigned to that planned time point).

### **7.8.3      Vital signs**

Descriptive statistics over time including change from baseline will be performed for vital signs (BP, PR, RR and body temperature).

Descriptive statistics will be calculated by planned time point based on the last value of the subject at that planned time point (or assigned to that planned time point).

### **7.8.4      ECG**

#### **Continuous safety ECG monitoring (by investigator)**

Clinically relevant abnormal findings will be reported as AEs.

No separate listing or analysis of continuous ECG monitoring will be prepared.

#### **12-lead ECG**

Abnormal findings, irrespective of whether they originate from central or local evaluation, will be reported as baseline conditions (at screening) or as AEs (during the trial) if judged clinically relevant by the investigator.

All evaluations of ECG data will be based on the TS, except the exposure-response analyses, which are based on the ECGPCS set.

#### **Listing of individual data**

For all quantitative endpoints, listings of individual data will be shown in Appendix 16.2. For QTcB and RR only listings will be provided. Occurrences of notable findings will be flagged.

Comments regarding the ECGs will be listed.

#### **Categorical endpoints**

For the categorical endpoints, frequency tables will be provided.

For all subjects with any notable finding in ECG intervals, a separate listing will be created as end-of-text display (based on the same display template as in Appendix 16.2), and the corresponding time profiles will be shown.

#### **Quantitative endpoints**

Descriptive statistics (N, mean, SD, min, median, max) will be provided for the changes from baseline over time of QTcF, HR, QT, PR and QRS. The time profiles of mean and SD for the changes from baseline on treatment will be displayed graphically by treatment.

For QTcF and HR changes from baseline, the relationship to the corresponding plasma concentrations will be evaluated using a random coefficient model. For subjects in the

ECGPCS, all time points with available ECG endpoints and valid time-matched drug plasma concentrations will be included. For the handling of missing values, see [Section 6.6](#).

The response variable will be the change from baseline in QTcF ( $\Delta$ QTcF). The placebo subjects will be included in the analysis, setting their plasma concentrations to zero.

As a first step, it is investigated if there is a potential delayed or accelerated (e.g. due to metabolites) effect of the drug on QTcF. A general visual impression will be provided by overlaying time profiles of plasma concentrations and QTcF changes from baseline ( $\Delta$ QTcF). These figures will be generated for each subject (presented in Statistical Appendix of the CTR), as well as for means per active treatment (presented in the End-of-Text part of the CTR).

The relationship between BI 730357 plasma concentrations and QTcF changes from baseline will be investigated in an exploratory manner using a random coefficient model to estimate the difference in means between BI 730357 and placebo of QTcF change from baseline and its 90% confidence interval at the geometric mean of  $C_{max}$  for each dose. Additionally, the estimated overall slope with its 90% confidence interval will be provided. The used random coefficient model is based on a white paper from Garnett et al. ([12](#)) with  $\Delta$ QTcF as response variable, centered baseline QTc and plasma concentration as continuous covariates, treatment and time as fixed categorical effects, and a random intercept and slope for each subject. For more details refer to [Section 9.3](#).

For visualization, a scatterplot of the BI 730357 plasma concentration against the following individual QTcF values will be provided: For each subject on active treatment and each time point, subtract the mean value of all individual observed  $\Delta$ QTcF values from the placebo group for this time point from the individual observed  $\Delta$ QTcF value for this subject and time point. This results in estimates for “individual  $\Delta\Delta$ QTcF” values, which should only be used for plotting purposes. The corresponding regression line and its pointwise confidence bands as well as and the geometric mean of  $C_{max}$  for each dose will additionally be displayed in the plot.

To check model assumptions, the conditional residuals will be plotted and presented in the Statistical Appendix of the CTR. In case of non-linearity or if there is evidence for a delayed effect, further models will be explored in order to better characterise the PK-ECG relationship (e.g. effect compartment models, non-linear models, etc.).

All of the above described graphical and statistical analyses will be also performed for HR in place of QTcF.

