## FLOW CHART

Visit	Day	Planned time (relative to drug administration [h:min])	Approximate clock time of actual day [h:min]	Event and comment	Safety laboratory test	Exclusionary laboratory tests	PK blood 	12-lead ECG	4 hours continuous 3-lead ECG monitoring 	Vital signs 	Questioning for AEs and concomitant therapy 
1	-28 to -2			Screening 	x	x					
2	-1	-12:00 	21:00	Ambulatory visit, Admission to trial site	x	x 				x	
	1	-3:00	06:00	Allocation to treatment (randomisation) 	x 		x 			x 	
		0:00	09:00	Drug administration (with app. 240 mL water)						▲	x
		0:30	09:30				x			x 	x 
		1:00	10:00				x			x	x
		1:30	10:30				x			x	x
		2:00	11:00	App. 240 mL fluid intake			x			x	x
		2:30	11:30				x				
		3:00	12:00				x			x	x
		4:00	13:00	App. 240 mL fluid intake, thereafter lunch	x		x			x 	x
		5:00	14:00				x			x 	x
		6:00	15:00				x			x 	x
		8:00	17:00				x			x 	x
		10:00	19:00	Dinner 			x			x 	x
		12:00	21:00				x			x 	x
	2	24:00	09:00	Breakfast 	x		x			x	x
		28:00	13:00	Lunch 						x	
		34:00	19:00				x			x	x
		34:30	19:30	Dinner 						x	x
	3	48:00	09:00	Breakfast  , discharge from trial site			x			x	x
	4	72:00	09:00	Ambulatory visit 			x			x	x
	5	96:00	09:00	Ambulatory visit 			x			x	x
	8	168:00	09:00	Ambulatory visit 	x		x			x	
3	9 to 13			End of study (EOS) examination 	x			x	x	x	x

AE: adverse event, app.: approximately, ECG: Electrocardiogram, PK: pharmacokinetic(s)

1. Subject must be informed and written informed consent obtained prior to starting any screening procedures. Screening procedures (28 to 2 days before drug administration) include physical examination, check of vital signs, ECG, safety laboratory test, exclusionary laboratory tests (including drug screening, infection serology, and alcohol breath test), demographics (including determination of body height and weight), relevant medical history, concomitant therapy and review of inclusion/exclusion criteria. Screening procedure should complete prior to Visit 2.

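### The SAP's check for a delayed QTcF effect overlays concentration with QTcF changes that are not placebo-corrected, so a drift shared by all subjects can mimic or mask a delay and misdirect the exploration of further models

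*SAP*

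**What the plan says.** SAP 7.8.4 (Quantitative endpoints) opens the concentration-QTcF analysis with a look for a delayed or accelerated effect: "A general visual impression will be provided by overlaying time profiles of plasma concentrations and QTcF changes from baseline". There are two sets of figures. For the individual ones, "These figures will be generated for each subject (presented in Statistical Appendix of the CTR"; the mean ones are "as well as for means per active treatment (presented in the End-of-Text part of the CTR". SAP 6.7 defines the ECG baseline as the mean of the one triplicate taken before dosing.

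The check has a consequence later in the same section: "In case of non-linearity or if there is evidence for a delayed effect, further models will be explored", with effect compartment and non-linear models as examples.

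Elsewhere the section allows for changes over time that are not due to drug:
- The random coefficient model has "treatment and time as fixed categorical effects" and includes placebo subjects at concentration zero.
- The concentration scatterplot uses ΔΔQTcF. For each active subject and time point the SAP will "subtract the mean value of all individual observed" ΔQTcF values on placebo at that time.
- Mean ΔQTcF profiles are drawn by treatment, but without concentration and without any link to the delay check.

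All of this is repeated for heart rate.

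**The concern.** Everyone follows the same clock. The Protocol Flow Chart puts dosing at about 09:00 and, at 4 h, "App. 240 mL fluid intake, thereafter lunch"; dinner is at 10 h. Meals come last when several actions share a time point, so the 4 h ECG is still fasted and the 6 h ECG is the first after food. The single baseline is a fasted early-morning value. Any effect of food or time of day on QTcF therefore stays in ΔQTcF at 6, 8 and 12 h, at the same post-dose times in every dose group. Agreement across the three doses gives no protection.

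A hysteresis check looks for a QTcF peak that comes later than the concentration peak. A shared upward drift after lunch produces that pattern with no delay in the drug effect, and a downward drift can hide a real delay. At stake is whether further models are explored for the right reason.

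**Working it through.** **No figure to reproduce.** The documents give no SD, drift size, tmax or numerical rule for delay. The sizes below are illustrations on stated assumptions. The group sizes are the plan's own (SAP 6.1 and 7): 6 active subjects per dose and 3 × 2 = 6 pooled placebo. After dosing, one ECG per time point is read centrally (SAP Table 6.7: 1).

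**Check 1: no drug effect**

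Assumptions: single-ECG SD 7 ms, independent between times; a common drift reaching A ms at 8–12 h; contrast = mean of two late ECGs minus the one ECG at Cmax (4 h); a rise above 4 ms is read as delay. The baseline is the same at all times and cancels in the contrast.

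- Variance per subject: 7² × (1/2 + 1) = 73.5 ms².
- SD of the contrast, raw mean of one dose group: √(73.5/6) = 3.50 ms.
- SD of the contrast, placebo-corrected: √(73.5 × (1/6 + 1/6)) = 4.95 ms, which is √2 ≈ 1.41 times larger.
- Spurious rise under the assumed drift shape: 2.3, 3.8 and 6.0 ms for A = 3, 5 and 8 (taken from simulation). The expected corrected rise is 0 in each case.
- Raw chance = 1 − Φ((4 − rise)/3.50). Corrected chance = 1 − Φ(4/4.95) = 1 − Φ(0.81) = 21%.

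| Drift A (ms) | Rise (ms) | z, raw | Raw | Corrected |
|---|---|---|---|---|
| 0 | 0 | 1.14 | 13% | 21% |
| 3 | 2.3 | 0.49 | 31% | 21% |
| 5 | 3.8 | 0.06 | 48% | 21% |
| 8 | 6.0 | −0.57 | 72% | 21% |

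The two displays break even where (4 − rise)/3.50 = 4/4.95, that is, rise = 4 − 3.50 × 0.808 = 1.17 ms. Since the rise is about 0.76 A, this is a drift of roughly 1.5 ms. Below it the raw profile gives fewer false alarms; above it the corrected profile does.

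**Check 2: a direct drug effect**

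This simulation used 10,000 runs at the SAP's ECG times, with 6 active and 6 placebo subjects. Assumptions: concentration peak at 4 h, half-life 20 h, direct effect of 5 ms, SD of ΔQTcF 6 to 10 ms, drift at 6–8 h equal in both arms. The contrast is the mean at 6–8 h minus the mean at 2–4 h, and 3 ms or more counts as delay.

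| Drift (ms) | Raw, SD 6 to SD 10 | Corrected, SD 6 to SD 10 |
|---|---|---|
| 0 | 8% to 19% | 16% to 27% |
| 5 | 79% to 69% | 16% to 27% |
| 8 | 99% to 90% | 16% to 27% |

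A drift of only 3 ms moves the peak of the expected raw curve: 5 × 1.00 = 5.0 ms at 4 h against 5 × 0.96 + 3 = 7.8 ms at 6 h.

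**Check 3: masking**

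Take a true delayed effect (effect compartment, rate 0.25/h, peak 5 ms). Its expected fractions of peak are 0.87 and 0.97 at 6 and 8 h, and 0.30, 0.50 and 0.66 at 2, 3 and 4 h. The true contrast is 5 × (0.92 − 0.487) = +2.2 ms. A drift of −5 ms at 6–8 h turns it into −2.8 ms, so no delay is visible in that window.

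**The case against.** The strongest reply is that little depends on this figure. The SAP commits to the random coefficient model, its slope and its estimate at the geometric mean Cmax, each with a 90% interval, whatever the overlay shows. Further models are only explored, within an analysis that is itself exploratory. A reader might infer that a drift could cause the linear model to be dropped, or bias its reported slope and effect at Cmax. The documents do not support that: no rule removes the model, and its categorical time effect together with the placebo subjects absorbs a common drift. This part of the objection stands.

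A reader might also infer that placebo is left out of every overlay. Only the mean figures are restricted to active treatments. The individual figures are for each subject and do not exclude placebo, although placebo subjects have no drug concentration profile to set beside their QTcF. The by-treatment ΔQTcF profiles would show a placebo drift, and the residual plots, mentioned just before the sentence on further models, come from a time-adjusted model. A careful analyst could use both. But the SAP does not say that either is used to judge delay, and the overlay is the only display it names for that purpose.

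Third, correction has a price: with little or no drift the corrected profile gives more false alarms. The same placebo mean is also subtracted from all three doses, so a chance movement in 6 subjects appears in each of them. This stands too, and it rules out replacing the raw overlay.

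Pooling the 18 active subjects would give a sharper contrast between the displays, but the SAP plots means per dose, so 6 is the relevant number.

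**Conclusion.** The point holds in a limited form. The overlay named for judging delay keeps a drift that the same section removes in its model and its scatterplot. The error is directional: it can point to a delay that is not there, or hide one. It affects the decision to explore further models, not the prespecified estimates.

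Under the assumptions of Check 1, the chance of a spurious late rise in a dose-group mean is 31% to 72% raw for drifts of 3 to 8 ms, against 21% corrected, and 13% against 21% with no drift. Drift size and shape, SD, time of Cmax and the 4 ms cut-off are all assumptions. That a common drift biases the raw profile and cancels in expectation from the corrected one does not depend on them. SAP Section 9.3, cited for model details, is not in the available text and may say more about how delay is assessed. This is a worthwhile, inexpensive improvement to an exploratory analysis.

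**What to change.** In SAP 7.8.4, add two series to the mean overlay for each dose: the pooled placebo mean ΔQTcF profile, and the mean ΔΔQTcF formed from the values already derived for the scatterplot. Keep the raw ΔQTcF series. State that evidence for a delayed or accelerated effect is judged from the raw and placebo-corrected profiles together. Make the same change for heart rate.

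The cost is a few lines of SAP text and two more plotted series, with no new data or visits. The downside is noise: under the 7 ms assumption the SD of the late-minus-Cmax contrast is 4.95 ms on the corrected profile against 3.5 ms raw. That is why neither profile should decide alone.
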